2. TYPE OF PLANNED ANALYSIS

2.1. DMC Interim Analyses

An external multidisciplinary data monitoring committee (DMC) reviewed the progress of the study, performed interim reviews of safety data at regular intervals, and provided recommendation to Gilead on whether the nature, frequency, and severity of AEs associated with study treatment warrant the early termination (ET) of the study in the best interests of the patient, whether the study should continue as planned, or whether the study should continue with modifications.

In addition, the DMC has reviewed the results from the 1st planned interim efficacy analysis and will review the results from the 2nd planned interim efficacy analysis. Based on the pre-specified superiority and futility rules, the DMC may make recommendations to Gilead on whether the study should be stopped early due to overwhelming efficacy, be terminated for futility, or continue as planned. Efficacy superiority boundaries are specified in Table 2-1 and non-binding futility rules are specified in Table 2-2.

The DMC's specific activities were defined by a mutually agreed unpon charter, which defined the DMC's membership, conduct, and meeting schedule.

While the DMC will be asked to advise Gilead regarding future conduct of the study, including possible early study termination, the ultimate decision on whether to implement or act based upon the recommendations of the DMC will be made by Gilead.

The study protocol specified 2 interim efficacy analyses conducted and evaluated by the DMC.

The first DMC interim efficacy analysis was conducted at 8 months after 348 patients had been randomized (data cut date: 12Aug2022). At that time, 144 deaths (39.6% of 364 deaths) were observed.

The second planned interim efficacy analysis will be conducted when approximately 257 deaths (71% of 364 deaths) have occurred, outstanding data queries have been resolved or adjudicated as unresolvable, and the data have been cleaned and finalized. In the case that the null hypothesis on CR rate was not rejected based on the first 348 randomized patients in the first interim analysis at a 2-sided significance level of 0.03, a non-binding futility analysis with a futility boundary of HR = 0.95 will be performed at the second planned interim analysis.

- If the null hypothesis on CR based on the first 348 randomized patients was rejected in the first interim analysis at a 2-sided significance level of 0.03, $\alpha = 0.05$ (2-sided) will be allocated to the analysis of OS and key secondary endpoints in the first interim, second interim, and final analyses
- If the null hypothesis on CR rate based on the first 348 randomized patients was not rejected in the first interim analysis at a 2-sided significance level of 0.03, $\alpha = 0.02$ (2-sided) will be allocated to the analysis of OS and key secondary endpoints in the first interim, second interim, and final analyses

The Lan-DeMets approach with O'Brien-Fleming type alpha spending function are used for the first and second interim analyses, and final analysis for OS. The stopping boundaries at each analysis time are provided in Table 2-1.

		Efficacy		Stopping Boundary	
Planned Analyses		Analysis Events (%)		HRª	Two-sided p-value
First IA	λ	CR	-	-	0.03
	First IA	OS	144 ^b (40%)	0.570	0.000732
If the test of CR is rejected in	Second IA	OS	257 (71%)	0.738	0.0150*
first IA	Final Analysis	OS	364 (100%)	0.811	0.0453*
	First IA	OS	144 (40%)	0.519	0.000084
If the test of CR fails to be rejected in first IA	Second IA	OS	257 (71%)	0.700	0.0043*
	Final Analysis	OS	364 (100%)	0.781	0.0186*

 Table 2-1.
 Stopping Boundaries for Efficacy Superiority Analyses

HR = hazard ratio, IA = interim analysis, OS = overall survival, CR = complete remission

a HR presented in the table is 1-sided (lower) efficacy boundary.

b 144 deaths were observed at first interim efficacy analysis (data cut date: 12Aug2022).

* The boundary p-values at each analysis timepoint will be based on the actual observed events and adjusted by using the Lan DeMets approach with O'Brien-Fleming type alpha spending function.

Table 2-2.Non-Binding Futility Boundaries

			Non-Binding Futility Boundary
Planned Analyses		Efficacy Analysis	HR
If the test of CR fails to	First IA	OS	0.99
be rejected in first IA	Second IA	OS	0.95

HR = hazard ratio, IA = interim analysis, OS = overall survival

The primary efficacy endpoint of OS will be tested for superiority first at the significance level specified in Table 2-1. If the superiority of OS is established, key secondary efficacy endpoints listed in Table 2-3 will be tested for superiority. To strongly control the overall type I error across the testing of the key secondary efficacy endpoints, a hierarchical testing strategy will be performed with a predefined order as listed below. For each key secondary endpoint, an O'Brien-Fleming boundary will be derived based on the information fraction at each interim analysis and the remaining type I error respectively per Table 2-3.

Endpoint	Information Fraction at the Interim Analysis
ORR	Proportion of patients who have at least 8 months follow-up since randomization (including patients who have early discontinued, are lost to follow-up, or have died)
RBC transfusion independence rate	Proportion of patients who have at least 8 months follow-up since randomization (including patients who have early discontinued, are lost to follow-up, or have died)
EFS	40% at the first interim analysis, 71% at the second interim analysis (same with those of OS)*
CR in TP53 mutant population	Proportion of patients who have at least 8 months follow-up since randomization (including patients who have early discontinued, are lost to follow-up, or have died)
MRD-negative response	Proportion of patients who have at least 8 months follow-up since randomization (including patients who have early discontinued, are lost to follow-up, or have died)
Time to transformation to AML	40% at the first interim analysis, 71% at the second interim analysis (same with those of OS)*
PFS	40% at the first interim analysis, 71% at the second interim analysis (same with those of OS)*
FACT-Anemia response rate	Proportion of patients who have at least 8 months follow-up since randomization (including patients who have early discontinued, are lost to follow-up, or have died)

Table 2-3.Definition of Information Fraction

AML = acute myeloid leukemia; EFS = event-free survival; FACT-Anemia = Functional Assessment of Cancer Therapy-Anemia; MRD = minimal residual disease; ORR = objective response rate; OS = overall survival, PFS = progression free survival

*The information fraction at each analysis timepoint will be based on the actual observed OS events

The key secondary endpoints will be tested in the following order:

- ORR
- RBC transfusion independence rate
- EFS
- CR in TP53 mutant population
- MRD-negative response
- Time to transformation to AML
- PFS
- FACT-Anemia response rate

Version 1.0

A given hypothesis can only be tested and declared statistically significant if all previous hypotheses tested in the hierarchy are also statistically significant.

2.2. Optional Interim Analysis Performed by Sponsor

At the time of the second interim efficacy analysis, if the efficacy superiority boundary of OS has been crossed, the Sponsor study team may be unblinded for the entire ITT Analysis Set by the data cutoff date and will conduct the efficacy and safety analyses. Gilead Oversight Committee will make the decision on whether study team will be unblinded.

2.3. Final Analysis

If the null hypothesis on OS is not rejected in either of the 2 planned interim analyses, the final unblinded efficacy analysis will be conducted when approximately 364 OS events have occurred, outstanding data queries have been resolved or adjudicated as unresolvable, and the data have been cleaned and finalized.

If the null hypothesis on OS is rejected in any planned interim analyses, the timing of the final analysis may be driven by the data maturity of all efficacy data and the need of the safety evaluation update.

3. GENERAL CONSIDERATIONS FOR DATA ANALYSES

Analysis results will be presented using descriptive statistics. For categorical variables, the number and percentage of patients in each category will be presented; for continuous variables, the number of patients (n), mean, standard deviation (StD) or standard error (SE), median, first quartile (Q1), third quartile (Q3), minimum, and maximum will be presented.

By-subject listings will be presented for all patients in the Intent-to-Treat (ITT) Analysis Set and sorted by subject ID number, visit date, and time (if applicable). Data collected on log forms, such as AEs, will be presented in chronological order within the subject. Age, sex at birth, race, and ethnicity will be included in the listings, as space permits.

3.1. Analysis Sets

Analysis sets define the patients to be included in an analysis. Analysis sets and their definitions are provided in this section. The analysis set will be identified and included as a subtitle of each table, figure, and listing.

For each analysis set, the number and percentage of patients eligible for inclusion will be summarized by treatment group.

A listing of reasons for exclusion from analysis sets will be provided by subject.

3.1.1. Intent-to-Treat (ITT) Analysis Set

The ITT Analysis Set includes all patients who were randomized in the study, with treatment assignment designated according to the treatment to which the subject is randomized. This is the primary analysis set for efficacy analyses.

3.1.2. Safety Analysis Set

The Safety Analysis Set includes all randomized patients who took at least 1 dose of any study treatment, with treatment assignment designated according to the actual treatment received. This is the primary analysis set for safety analyses.

3.1.3. Pharmacokinetic Analysis Set

The Pharmacokinetic (PK) Analysis Set will include all patients who took at least 1 dose of Magrolimab, and have at least 1 measurable post-treatment serum concentration of magrolimab. This is the primary analysis set for all PK analyses.

3.1.4. Immunogenicity Analysis Set

The Immunogenicity Analysis Set will include all patients who took at least 1 dose of Magrolimab, and have at least 1 reported anti-drug antibody (ADA) result.

3.2. Subject Grouping

For analyses based on the ITT Analysis Set, patients will be grouped according to the treatment to which they were randomized. For analyses based on the Safety Analysis Set, patients will be grouped according to the actual treatment received. The actual treatment received will differ from the randomized treatment only when their actual treatment differs from randomized treatment for the entire treatment duration.

For the PK Analysis Set and the Immunogenicity Analysis Set, patients will be grouped according to the actual treatment they received.

3.3. Strata and Covariates

Patients will be randomized in a 1:1 ratio to treatment arms using an interactive voice/web/mobile response system (IXRS) with a stratified randomization schedule. Stratification will be based on the following variables:

- geographic region (US versus ex-US sites)
- cytogenetic risk status (very good/good/intermediate versus poor/very poor versus unknown) according to IPSS-R
- percentage of baseline bone marrow blasts ($\geq 10\%$ versus < 10% blasts)

If bone marrow blasts stratification factor value is not recorded in the clinical database, the value recorded in the IXRS will be used for analyses. If there are discrepancies in stratification factor values between the IXRS and the clinical database, the values recorded in the clinical database will be used for analyses. Additionally, stratification discrepancies will be reviewed and assessed. Based on the assessment of stratification discrepancies, a sensitivity analysis of the primary endpoint may be performed.

Efficacy endpoints will be evaluated using stratification factors as covariates or stratification variables for analyses when applicable, as specified in Section 6. If there is an imbalance in presumed prognostic baseline characteristics between treatment groups, efficacy evaluations may be performed that include these baseline values in efficacy analysis models as covariates; these evaluations will be considered as sensitivity analyses.

In the situation where there is insufficient information in a stratum, pooling of the stratum with the smallest adjacent stratum for stratified analyses will be considered.

3.4. Examination of Subject Subgroups

The primary efficacy endpoints will be examined using the following subgroups:

• geographic region (US versus ex-US sites)

- cytogenetic risk status (very good/good/intermediate versus poor/very poor versus unknown) according to IPSS-R
- percentage of baseline bone marrow blasts ($\geq 10\%$ versus < 10% blasts)

The analysis may also be conducted in the subgroups by TP53 mutational status (mutant and wild type), age (< 65 years and \geq 65 years; < 75 years and \geq 75 years), sex at birth (male and female), race (White, Asian, Black, Other), IPSS-R (Intermediate, High, Very high), baseline ECOG (0, 1, and 2), disease type (non-therapy related vs therapy-related).

If the number of subjects in one or more subgroups is too small to conduct the analysis, some subgroups will be pooled for the analysis.

3.5. Multiple Comparisons

The Multiple Comparisons are provided in Section 2.1.

3.6. Missing Data and Outliers

3.6.1. Missing Data

In general, missing data will not be imputed unless methods for handling missing data are specified. Exceptions are presented in this document.

The handling of missing or incomplete dates for disease diagnosis is described in Section 5.3, for the death date and the start date of new anticancer therapy in Section 6.1.1, for AE onset in Section 7.1.5.2, and for prior and concomitant medications in Section 7.4.

3.6.2. Outliers

Outliers will be identified during the data management and data analysis process, but no sensitivity analyses will be conducted. All data will be included in the data analysis.

3.7. Data Handling Conventions and Transformations

The following conventions will be used for the imputation of date of birth when it is partially missing or not collected:

- If only month and year of birth is collected, then "15" will be imputed as the day of birth
- If only year of birth is collected, then "01 July" will be imputed as the day and month of birth
- If year of birth is missing, then date of birth will not be imputed

In general, age collected at Day 1 (in years) will be used for analyses and presented in listings. If age at Day 1 is not available for a subject, then age derived based on date of birth and the Day 1 visit date will be used instead. If an enrolled subject was not dosed with any study drug, the randomization date will be used instead of the Day 1 visit date. For screen failures, the date the first informed consent was signed will be used for the age derivation. Age required for longitudinal and temporal calculations and analyses (eg, estimates of creatinine clearance, age at date of AE) will be based on age derived from date of birth and the date of the measurement or event, unless otherwise specified.

Non-PK data that are continuous in nature but are less than the lower limit of quantitation (LOQ) or above the upper LOQ will be imputed as follows:

- A value that is 1 unit less than the LOQ will be used to calculate descriptive statistics if the datum is reported in the form of "< x" (where x is considered the LOQ). For example, if the values are reported as < 50 and < 5.0, values of 49 and 4.9, respectively, will be used to calculate summary statistics. An exception to this rule is any value reported as < 1 or < 0.1, etc. For values reported as < 1 or < 0.1, a value of 0.9 or 0.09, respectively, will be used to calculate summary statistics.
- A value that is 1 unit above the LOQ will be used to calculate descriptive statistics if the datum is reported in the form of "> x" (where x is considered the LOQ). Values with decimal points will follow the same logic as above.
- The LOQ will be used to calculate descriptive statistics if the datum is reported in the form of "≤ x" or "≥ x" (where x is considered the LOQ).

If methods based on the assumption that the data are normally distributed are not adequate, analyses may be performed on transformed data or nonparametric analysis methods may be used, as appropriate.

3.8. Analysis Visit Windows

3.8.1. Definition of Study Day

Study day will be calculated from the first dosing date of any study drug, which is the date of the first dose of magrolimab/placebo, or azacitidine, whichever occurs first and derived as follows:

- For postdose study days: Assessment Date First Dosing Date + 1
- For days prior to the first dose: Assessment Date First Dosing Date

Therefore, study day 1 is the day of first dose of study drug administration. If the subject is randomized but not dosed, the randomization date will be study day 1.

3.8.2. Analysis Visit Windows

Subject visits might not occur on protocol-specified days. Therefore, for the purpose of analysis, observations will be assigned to analysis windows. The analysis windows for lab are provided in Table 3-1.

		Visit Window Study Day		
Analysis Visit	Nominal Study Day	Lower Limit	Upper Limit	
Baseline			1 ^a	
Week 1	8	1 ^b	11	
Week 2	15	12	18	
Week 3	22	19	25	
Week 4	29	26	32	
Week 5	36	33	39	
Week 6	43	40	46	
Week 7	50	47	53	
Week 8	57	54	63	
Week 10	71	64	77	
Week xx	xx*7+1	(xx-1)*7+1	(xx+1)*7	

Table 3-1.Analysis Visit Windows for Lab By-visit Summaries

a Prior to first dose date time.

b Post first dose date time.

The analysis windows for PRO are provided in Table 3-2.

 Table 3-2.
 Analysis Visit Windows for By-visit Summaries of PRO assessments

Analysis Visit	Nominal Study Day	Visit Window Study Day	
		Lower Limit	Upper Limit
Baseline			1
Week 4	29	2	42
Week 8	57	43	70
Week 12	85	71	98
Week xx	xx*7+1	xx*7-13	xx*7+14

For any data relating to unscheduled visits, the following will be made:

- An unscheduled visit prior to the first dosing of any study drug will be included in the calculation of the baseline value, if applicable.
- Unscheduled visits after the first dosing of any study drug will be included in determining the maximum postbaseline toxicity grade and anti-magrolimab antibody status.
- Response assessments and PRO assessments performed at unscheduled visits after the date of randomization will be included in the analyses of the efficacy endpoints and the PRO related endpoints, respectively.

3.8.3. Selection of Data in the Event of Multiple Records in an Analysis Visit Window

If multiple valid, nonmissing measurements exist in an analysis window, records will be chosen based on the following rules if a single value is needed:

- For baseline, the last nonmissing value on or prior to the first dosing date of study drug (and prior to first dosing time) will be selected, unless specified differently. If there are multiple records with the same time or no time recorded on the same day, the baseline value will be the arithmetic average of the measurements for continuous data, or the measurement with the lowest severity for categorical data.
- For postbaseline values:
 - The record closest to the nominal day for that visit will be selected.
 - If there are 2 records that are equidistant from the nominal day, the later record will be selected.
 - If there is more than 1 record on the selected day, the arithmetic average will be taken for continuous data and the worse severity will be taken for categorical data, unless otherwise specified.

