Dose Schedule	Priming Dosing											Maintenance Dosing	
	None		± 3									± 3	
Visit Window (Days)	1	2	4	8	11	15	22	29	36	43	50	57	every 2 Weeks thereafter
Pregnancy test ^a	X							X				X Q4W	
CBC with differential, platelets, reticulocytes ^{b,c,d}	X ^e	X	X ^e	X	X	X	X	X	X	X	X	X	X
Haptoglobin and LDH ^c	X			X				X					
Serum or plasma chemistry ^{b,c}	X			X		X	X	X		X		X	X
Peripheral smear ^{c,f}	X	X			X								
Peripheral blood sample for biomarker studies ^g	X			X				X				X ^h	
PK ^g	X			X				X				X ⁱ	
Antidrug antibodies ^{c,j}	X							X				X ⁱ	
Vital signs ^k	X		X	X	X	X	X	X	X	X	X	X	X
Symptom-directed physical examination ^{b,c}	X			X		X		X				X	X
Adverse events	X	X	X	X	X	X	X	X	X	X	X	X	X
Blood transfusion	X	X	X	X	X	X	X	X	X	X	X	X	X
Concomitant medications	X	X	X	X	X	X	X	X	X	X	X	X	X
Premedication ^l	X		X	X	X								
Magrolimab or placebo ^m	X ⁿ		X ⁿ	X	X	X	X	X	X	X	X	X	X

Abbreviations: CBC = complete blood count; D = day; EOT = end of treatment; LDH = lactate dehydrogenase; MRD = minimal residual disease; PK = pharmacokinetic(s); PRO = patient-reported outcome; Q4W = every 4 weeks; WBC = white blood cell.

- a Screening pregnancy test may be used if performed within 72 hours of first dose; pregnancy tests will be conducted once every month; additional guidance is provided in Section 5.1.1.
- b If magrolimab and azacitidine are administered on the same day, only one such study assessment is needed. Assessments should be performed prior to study treatment administration. For monitoring of infusion-related reactions, please refer to Section 6.5

- c Pretreatment assessments for the initial dose may be collected up to 72 hours before administration of study treatment; thereafter, pretreatment assessments are to be collected within 24 hours prior to study treatment administration.
- d Additional samples for CBC may be collected outside of the protocol-specified time points to ensure a WBC level $\leq 20 \times 10^3/\mu\text{L}$ prior to each magrolimab/placebo dose during the first 28 days of magrolimab priming dose. Peripheral blasts should be included in the CBC assessments.

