7.1.7. Additional Analysis of Adverse Events

7.1.7.1. Treatment-Emergent Adverse Events (TEAE) of Special Interest

Number and percentage of subjects with the following AEs of special interest will be summarized by PT:

- Anaemia (MST Anemia Extravascular Transient Hemolysis)
- Infusion Related Reaction (IRR) (SMQ-Hypersensitivity Narrow Terms) + within one day of latest infusion
- Transfusion reactions due to magrolimab interference with RBC typing (Gilead's MST)
- Thromboembolic Events (SMQ- Embolic and Thrombotic Events Broad Terms)
- Pneumonitis (SMQ- Interstitial Lung Disease Broad Terms)

Number and percentage of subjects with the following AEs of special interest will also be summarized by first AE onset time within 2 weeks, >2 weeks to 2 months, >2 months to 6 months, >6 months to 12 months, and >12 months of first dosing of any study drug:

- Anaemia
- IRR
- Transfusion reactions due to magrolimab interference with RBC typing
- Thromboembolic Events
- Pneumonitis

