7.2. Laboratory Evaluations

Laboratory data collected during the study will be analyzed and summarized using both quantitative and qualitative methods. Summaries of laboratory data will be provided for the Safety Analysis Set and will include data collected up to the last dose of study drug plus 30 days or the day before initiation of new anticancer therapy including SCT (whichever is earlier). The analysis will be based on values reported in conventional units. When values are below the LOQ, they will be listed as such, and the closest imputed value will be used for the purpose of calculating summary statistics as specified in Section 3.7.

A by-subject listing for laboratory test results will be provided by treatment group, subject ID and visit in chronological order for hematology and serum chemistry separately. Values falling outside of the relevant reference range and/or having a severity grade of 1 or higher on the CTCAE severity grade will be flagged in the data listings, as appropriate.

Plots of lab parameters will include (but not limit to) hemoglobin, platelet, and absolute neutrophil counts across time.

No formal statistical testing is planned.

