7.2.1. Summaries of Numeric Laboratory Results

Descriptive statistics will be provided by treatment group for each laboratory test specified in the study protocol as follows:

- Baseline values
- Values at each postbaseline time point visit
- Postbaseline maximum value

- Postbaseline minimum value
- Change and percentage change from baseline at each postbaseline time point visit
- Change and percentage change from baseline to postbaseline maximum value
- Change and percentage change from baseline to postbaseline minimum value

A baseline laboratory value will be defined as the last measurement obtained on or prior to the date/time of first dose of any study drug. Change from baseline to a postbaseline visit will be defined as the postbaseline value minus the baseline value. The mean, median, Q1, Q3, minimum, and maximum values will be displayed to the reported number of digits; StD values will be displayed to the reported number of digits plus 1.

Median (Q1, Q3) of the observed values will be plotted using a line plot by treatment group and visit for the laboratory tests including but not limited to hemoglobin, platelet, and absolute neutrophil counts.

In the case of multiple values associated with a visit, data will be selected for analysis as described in Section 3.8.3.

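### Does the single Week 1 laboratory window hide the early hemoglobin drop after the first two doses?

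*SAP*

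**What the plan says.** Protocol Table 4 schedules blood counts on Days 1, 2, 4, 8, 11 and 15. Footnote e adds a hemoglobin check 3 to 6 hours after the start of doses 1 and 2 (Days 1 and 4). Footnote c governs when pre-dose samples are drawn after the first dose: "thereafter, pretreatment assessments are to be collected within 24 hours prior to study treatment administration".

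SAP Table 3-1 defines Week 1 as Day 1 (after the first dose) to Day 11, nominal Day 8, and Week 2 as Days 12 to 18, nominal Day 15. Where a single value is needed, SAP 3.8.3 gives the rule: "The record closest to the nominal day for that visit will be selected". Ties go to the later record. For same-day records, "If there is more than 1 record on the selected day, the arithmetic average will be taken for continuous data".

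SAP 7.2.1 carries these rules into the laboratory summaries: "In the case of multiple values associated with a visit, data will be selected for analysis as described in Section 3.8.3". By arm, it specifies values and changes at each visit and changes to the postbaseline maximum and minimum. It also specifies a plot: "Median (Q1, Q3) of the observed values will be plotted using a line plot by treatment group and visit for the laboratory tests". SAP 7.2 states more generally: "Plots of lab parameters will include (but not limit to) hemoglobin, platelet, and absolute neutrophil counts across time". Laboratory summaries "will include data collected up to the last dose of study drug plus 30 days", or to the day before new anticancer therapy if that is earlier.

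**The concern.** Anemia from CD47 blockade is the expected on-target toxicity, and the priming doses exist to soften it. Protocol 7.10.1.1 says drops of 2 to 3 g/dL or more have occurred in early doses and that complications of anemia could be life-threatening or fatal in participants with significant disease. The protocol requires hemoglobin on Days 1, 2 and 4, yet the by-visit rule sets those values aside in favour of Day 8.

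The other numeric summary that could catch an early low point, the change to minimum, runs over all of treatment plus 30 days. It cannot be tied to dose 1 or 2. If nothing else filled the gap, the placebo-controlled trial would collect the data for an early by-arm comparison and never tabulate it.

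**Working it through.** **Step 1: which record Week 1 keeps on the nominal schedule.** Distance = |study day − 8|.

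| Scheduled hemoglobin | Day | Distance |
|---|---|---|
| 3 to 6 h after dose 1 | 1 | 7 |
| Day 2 | 2 | 6 |
| Before dose 2 | 4 | 4 |
| 3 to 6 h after dose 2 | 4 | 4 |
| Before dose 3 | 8 | 0 |
| Before dose 4 | 11 | 3 |

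Day 8 is kept, so 1 of 6 values is used and 5 are not. Week 2 contains one scheduled value, Day 15. Through Day 15, 2 of 7 post-dose values enter the by-visit summaries.

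**Step 2: off the nominal schedule.** Drawing pre-dose samples the day before dosing (footnote c) puts the Day 8 visit at distance 0 or 1 and the Day 11 visit at 2 or 3, so Day 8 is still kept. The ±3-day visit window in Table 4 matters more. Take all ordered, non-consecutive placements of the Day 4, 8 and 11 visits within ±3 days, with the Day 4 visit no earlier than Day 3. There are 104. The Day 8 visit is kept in 84, the Day 11 visit in 13 and the Day 4 visit in 7 (84 + 13 + 7 = 104). The Day 1 post-dose and Day 2 values are never selected. These are counts of placements, not probabilities. If the Day 8 value is missing and the rest are on schedule, Day 11 (distance 3) is taken ahead of Day 4 (distance 4).

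**Step 3: what the kept value measures.** The Day 8 sample precedes dose 3. It falls 8 − 1 = 7 days after dose 1 and 8 − 4 = 4 days after dose 2. The Week 1 change from baseline is therefore a net g/dL change by arm after exactly two doses. Protocol 7.10.1.1 places the typical decline of about 0.5 to 1.5 g/dL in the first 1 to 2 weeks, the span that Weeks 1 and 2 report.

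**Step 4: other outputs that can draw on the early values.**

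| Output | SAP section | Early information by arm | Limit |
|---|---|---|---|
| Change to minimum | 7.2.1 | An early low point counts if it is the lowest | Not tied to a dose |
| Treatment-emergent abnormalities, Grade 3 or 4 | 7.2.2.2 | Worst grade | Not tied to a dose |
| Shift to worst grade | 7.2.4 | Worst grade | Not tied to a dose |
| Anaemia by first onset, starting with the first 2 weeks | 7.1.7.1 | Counts in a dated early period | Counts, not g/dL |
| Plots across time | 7.2 | Open wording, may use any times | No times specified |
| Listing | 7.2 | Individual results | No summary |

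**Step 5: what the protocol promised.** Protocol 8.6.3 commits, for select laboratory parameters, to changes over time, grade shifts from baseline to worst, and Grade 3 or higher abnormalities. The SAP supplies all three. In Table 4 and Section 6.4 the 3 to 6 hour checks lead directly to the instruction to transfuse as clinically appropriate. No analysis aim is attached to them.

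**The case for a change.** The best case for change is that Protocol 2.1.5.2 itself argues from this quantity. It gives an average decline of 0.4 g/dL with the priming dose in a combination study and describes no placebo comparison. Here a randomised comparison is available at the cost of a few descriptive rows, and none is specified. The substitutes are imperfect. The minimum mixes early loss with later myelosuppression from azacitidine, which both arms receive. Anaemia counts depend on investigator reporting, since Protocol 7.4 records a laboratory abnormality as an adverse event only if it needs active management. Day 8 can reflect transfusion, because anyone below 9 g/dL before dose 1 or 2 must be transfused.

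Part of this stands: the course within the first week is not summarised by arm. The gain from adding it is smaller than it seems:

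- Transfusion affects the added Day 4 values too, and baseline may itself follow a transfusion. The Day 1 recheck is the least exposed.
- A participant transfused and rechecked before dose 2 has two pre-dose values.
- SAP 3.8.1 counts study days from the first dose of either drug, while Protocol 6.7.1.2 lets magrolimab/placebo be delayed up to 3 days for a high white cell count. Rows labelled by study day need not follow dose 1.
- Separating pre-dose from post-dose values on Day 4 needs collection times, which the documents do not confirm.

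The added rows would describe the early course but would not isolate a drug effect on their own.

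**Conclusion.** No change is needed. On the nominal schedule the by-visit summaries set aside 5 of the 6 Week 1 hemoglobin values. What they report is still correct: a by-arm change after two doses at Week 1 and a further one at Week 2. The minimum, grade and shift outputs can use the early values, the anaemia onset table dates early events, and the listings show individual results. What is absent is a finer descriptive display for values collected to guide care at the bedside. One value per week is a fair trade-off for a by-visit table.

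The size of any early change left untabulated cannot be computed from the documents. No primary or secondary efficacy endpoint, and no type I error, is touched. If the safety team wants the early course, the open wording on plots in SAP 7.2 already allows it.

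This conclusion assumes visits close to schedule and that the Day 1 to 4 results are in the clinical database. With shifted visits the Week 1 record may instead be the Day 11 or Day 4 visit (13 and 7 of the 104 placements). That changes how many doses precede the Week 1 value, but not the conclusion.
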